While there is a paucity of data on the longer-term impact of iron supplementation (especially the use of IV iron) given to women in pregnancy, this study will enable us to describe correlations between women recruited in the 3 arms of the *RAPIDIRON Trial* as well as their hematologic, clinical, and overall health impact. These results will be additive to the critical primary outcome data generated on the offspring of these women.

General Growth and Nutrition

A secondary hypothesis of the *RAPIDIRON Trial* is that IV iron treatment early in pregnancy will reduce iron-deficiency-associated low birth weight (LBW) primarily due to premature delivery or intrauterine growth restriction. Both are risks for low iron stores at birth and poor postnatal growth in the offspring. Offspring born to mothers in the oral iron group, compared to the IV iron group, are more likely to be iron deficient during their fetal life, at birth, and during infancy. Prolonged iron deficiency can negatively impact linear growth. Chronic iron deficiency during the rapid phase of growth in infancy and early childhood results in vulnerability for growth impairment. Iron plays an important role in tissue oxygen delivery and transport of electrons within the cells, and iron acts as a co-factor for essential enzymatic reactions. Iron deficiency anemia likely delays growth by creating a hypoxic condition and inhibiting insulin-like growth factor-I (IGF-1). [14, 15] Hypoxemia due to iron deficiency anemia can also lead to an increase in hypoxia-induced growth factor (HIF-1 α), which in utero has been shown to decrease human growth hormone mRNA levels. [16] In infants and young children with iron deficiency anemia, iron therapy increased serum IGF-1 levels and growth velocity. [17] Several other studies have reported lower body weight, height, head circumference, and growth velocity in anemic children and improvement in growth parameters with iron therapy. [18, 19, 20]

The following general growth and nutrition assessments will be performed:

- *Standard anthropometrics* – weight, length (height), and head circumference will be measured at each of the six timepoints and plotted on the WHO standard pediatric growth curves. From these data, weight for age, length for age, and head circumference for age Z-scores will be generated and growth velocities will be calculated.
- *Nutritional survey* – the Infant and Child Feeding Index (ICFI) is a composite index used to measure feeding practices, which has been previously used in the Indian context and allocates scores based upon breastfeeding, dietary diversity, meal frequency, etc. [21] Data regarding iron-supplementation and iron-fortified foods will also be collected. This survey will be conducted at the birth, 6 week, 4 month, 12 month, and 24 month visits.

Maternal Secondary Outcomes

While the *RAPIDIRON-KIDS Study* represents an opportunity to understand the impact of two different approaches for the treatment of IDA during pregnancy on offspring, it also enables continued contact with a sample of *RAPIDIRON* participants. The interaction with these mothers during this follow-up study is an important means of appreciating the longer-term effects of the treatments used during the parent trial. As indicated in Table 1, the maternal secondary outcomes to be explored include the following: iron status when the offspring is 4, 12, and 24 months old; breastfeeding practices; quality of life, as measured by the World Health Organization Disability Assessment Schedule 2.0 (WHODAS 2.0); and rates of hospitalization and transfusion subsequent to the conclusion of the *RAPIDIRON Trial*.

E. Statistical Methods

Sample Size

We anticipate that at least 2,000 pregnant women will be recruited for the primary *RAPIDIRON Trial* across the three sites in Karnataka state and project that at least 600 complete data sets will be available for each of the three arms for analysis. Thus, an adequate number of infants per arm should be eligible for enrollment in the *RAPIDIRON-KIDS Study*. However, as demonstrated in the summary of the preliminary power analyses below, the aims of the *RAPIDIRON-KIDS Study* can be achieved by obtaining complete data sets for approximately 147 mother-offspring dyads for each of the three study arms (or a total of 441 dyads). Since *RAPIDIRON Trial* participants will be asked to consent to this follow-up study prior to delivery, we expect that some of them will experience a stillbirth or neonatal death and, thus, not

provide evaluable information on the infants. In addition, we expect that cord blood data will not be obtainable or analyzable for a certain percentage of live births resulting in missing data on two of the primary outcomes. To account for this, we plan on initially consenting approximately 525 *RAPIDIRON Trial* participants (~175 per arm). Because Aims 1 and 2 answer different essential research questions, the study is powered with a type I error rate of 0.05 for each of those aims.

We propose to conduct a total of four primary hypothesis tests for Aim 1. Two of those tests will be conducted on data collected at birth with separate tests comparing offspring born to mothers across both IV iron arms to those born to mothers in the oral arm with respect to hemoglobin level and log-transformed ferritin levels at birth. If either of those tests at birth show differences between the two arms, the comparable tests will be conducted at 4 months post-delivery. In all cases, the null hypothesis is that the mean across the IV arms is the same as that in the oral iron arm. To control the type I error rate across these two tests, the alpha level for each individual comparison will be 0.025. Although information on the likely effect sizes for the proposed intervention are insufficient to provide explicit estimates of power for this study, limited comparisons of infant hemoglobin levels in south Asian and Africa suggest that the differences in both hemoglobin levels and log ferritin levels in infants born to mothers with and without IDA differ by at least 0.8 standard deviations. Because we want to assure that this intervention is powered to detect effects somewhat smaller than that observed in mothers with and without IDA, we want to assure that this study has sufficient power to detect an effect that is in the range of 0.3 to 0.4 standard deviations. We anticipate that approximately 85% of the enrolled sample will provide data for our primary iron outcomes at birth. Thus, we estimate a sample size of at least 441 infants (147 per arm) will provide information at birth with a slightly higher number at 4 months as this time is not subject to difficulties with obtaining data from the cord blood at delivery. When evaluated in the context of the proposed mixed effects model where we assume an intraclass correlation coefficient of 0.5, a sample size of 147 per arm (294 IV iron vs. 147 oral) gives more than 80% power to detect a difference in means at birth of 0.31 standard deviations at the alpha=0.025 level. Since demonstrating the effects at 4 months requires that the hypothesis tests at birth reject the null hypothesis, the overall study power to detect a difference of 0.3 standard deviations or greater at 4 months is greater than 80%.

The primary outcome for Aim 2 is the Bayley Developmental Quotient (DQ) measured at 2 years of age. The average score across the two IV iron arms will be compared to the oral arm at the alpha=0.05 level. We expect to obtain data for approximately 85% of consented participants at this time point for a sample of at least 147 per arm. This sample size gives more than 90% power to detect a difference in means of 5 units on the BSID mean score assuming a standard deviation of 15 at the alpha=0.05 level. Because effect sizes in the range of 5 to 7.5 are generally clinically meaningful for the BSID, the study is well powered to detect clinically meaningful differences.

Primary Data Analysis

Statistical analyses involve both formal hypotheses testing for specified primary outcome measures and supportive descriptive analyses of secondary outcome measures.

Hemoglobin and log transformed ferritin will be separately modeled using mixed effects linear regression. Both outcomes will be measured at birth and 4 months, and hemoglobin will also be measured at 12 months. The mixed effects models will treat time as a categorical value and include fixed effects for time, treatment, and time by treatment interaction. Correlation among repeated measurements for each subject will be modeled through structuring the variance-covariance matrix of the residuals. Inclusion of the time by treatment interaction will allow for estimation of mean iron indices at each measurement time for each group. Within these models, the primary hypothesis tests for aim 1 will be performed by comparing the average across the two IV iron groups to the oral iron group with respect to the mean values at birth and at 4 months using a significance level of 0.025.

A similar mixed-effects model will be used for modeling Bayley DQ cognitive domain in participating children at 2 and 3 years of age. The primary test for aim 2 will be performed by comparing the average across the two IV arms to the oral iron arm at 2 years using a significance level of 0.05.

Secondary Analyses

Secondary analyses will examine the effect of the three treatment regimens on each of the secondary outcome measures including iron measures (hemoglobin, ferritin, reticulocyte hemoglobin content and % total iron binding saturation), neurodevelopmental measures (total score and scores for individual domains such as communication, fine motor, gross motor, problem solving ability, and personal-social functioning), preferential looking time (log transformed), scores for the four factors associated with the Behavioral Rating Scale (object orientation, motor quality, negative affect, and positive social responsiveness), T-scores for the CBCL/1.5-5 syndrome scales (Emotionally Reactive, Anxious/Depressed, Somatic Complaints, Withdrawn, Attention Problems, Aggressive Behavior, and Sleep Problems), the India Scale of Assessment for Autism, and the standard growth metrics (weight for age, length for age, and head circumference for age Z-scores). As noted previously, data from a nutritional survey will be collected; these data will only be included in analyses as potential effect modifiers or moderators, not as outcome measures. Maternal outcomes that include hematologic indices, a history of transfusion and/or hospitalization, and assessment of life quality are incorporated into this study as secondary analyses.

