Background: Anemia is a worldwide problem with iron deficiency being the most common cause. When anemia occurs in pregnancy, it increases the risk of adverse maternal, fetal and postnatal outcomes. It induces preterm births and low birth weight (LBW) deliveries, long-term developmental sequelae and an increased risk of earlier onset of postnatal iron deficiency. Anemia rates are among the highest in South Asia, and India's National Family Health Survey (NFHS-5) for 2019-21 indicated that over half of pregnant women, and more than 65% of children, in the country are classified as anemic: [1] In 2021, the *RAPIDIRON Trial* [2] was initiated in two states in India, with the goal of assessing if a dose of intravenous (IV) iron given to anemic women during pregnancy will result in a greater proportion of participants with normal hemoglobin concentrations in the third trimester and a lower proportion of participants with low birth weight deliveries compared to oral iron. As a follow-up to the *RAPIDIRON Trial*, the *RAPIDIRON-KIDS* study will follow the previously randomized mothers as well as their offspring after birth to assess neurodevelopmental, hematological, and health outcomes. This study's overarching goal is to determine if the offspring born to *RAPIDIRON Trial* mothers in the IV iron groups, compared to the oral iron group, will achieve superior neurodevelopment, iron stores, and growth at specific time points during the first three years of life.

A. Specific Aims

Hypotheses and Specific Aims

This study has two primary hypotheses as follows:

- (1) Infants born to *RAPIDIRON Trial* maternal participants from the intravenous (IV) iron arms will have higher hemoglobin and ferritin levels at birth (determined by cord blood) and at 4 months of age compared to infants born to mothers in the oral arm; and
- (2) Offspring born to *RAPIDIRON Trial* participants who received IV iron treatment will have higher developmental quotients (DQs) on the cognitive domain of the Bayley Scales of Infant Development (BSID) at 2 years of age compared to offspring born to *RAPIDIRON Trial* participants given oral iron treatment.

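### Aim 1: the 4-month power figure of above 80% at 0.3 SD is not reached for a given analyte (about 64%) and its meaning is undefined; the rule that opens the 4-month tests also needs one clear wording

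*Combined protocol and SAP*

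**What the plan says.** Section E, Sample Size, sets a type I error of 0.05 for Aim 1 and lists four primary tests: hemoglobin and log ferritin, each at birth and at 4 months. The 4-month tests depend on the birth tests: "If either of those tests at birth show differences between the two arms, the comparable tests will be conducted at 4 months post-delivery". On the level it says: "To control the type I error rate across these two tests, the alpha level for each individual comparison will be 0.025".

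The birth power statement concerns a single test: 147 per arm (294 IV versus 147 oral), intraclass correlation 0.5, more than 80% power at 0.31 SD and alpha 0.025. The stated aim is "sufficient power to detect an effect that is in the range of 0.3 to 0.4 standard deviations". The paragraph then reasons that "demonstrating the effects at 4 months requires that the hypothesis tests at birth reject the null hypothesis", and concludes that "the overall study power to detect a difference of 0.3 standard deviations or greater at 4 months is greater than 80" percent. The only information on the 4-month sample is that the infants counted at birth "will provide information at birth with a slightly higher number at 4 months".

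Hypothesis 1 in section A is that infants in the IV arms "will have higher hemoglobin and ferritin levels at birth (determined by cord blood) and at 4 months of age". Primary Data Analysis models the two analytes separately and compares the arms "with respect to the mean values at birth and at 4 months using a significance level of 0.025". It does not repeat the condition on the birth tests.

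**The concern.** The power sentence uses the need to reject at birth as its reason for power above 80% at 4 months. For the chance of ending with a 4-month claim, that requirement works the other way: a second condition can only lower it. The sentence does not say whether it means a given analyte, at least one, or both, nor whether the figure is joint with the birth result or conditional on it. It also leaves out the 4-month sample size, the effect assumed at birth and the sidedness. A reader cannot tell what the study promises for one of its primary questions.

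The opening rule has a smaller problem. One sentence lets either birth result open the comparable tests; a later one speaks of the birth tests, in the plural, rejecting. After a split result at birth, which 4-month tests are confirmatory could be decided with the birth results known.

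**Working it through.** **Inputs.** From Sample Size: 147 per arm, 294 versus 147; alpha 0.025; intraclass correlation 0.5, used here as the correlation between an infant's birth and 4-month values; 0.31 SD at birth and 0.3 SD at 4 months; about 175 per arm consented, the upper limit for the 4-month sample. Assumed, because the documents do not say: two-sided tests; equal effects at both times; hemoglobin-ferritin correlation from 0 to 0.8; correlation across both time and analyte equal to the product of the two.

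**1. The plan's birth figure.** SE = √(1/147 + 1/294) = 0.1010 SD; critical value 2.241. Power ≈ Φ(0.31/0.1010 − 2.241) = Φ(0.827) = 79.6%. This matches the stated figure of just over 80% to within rounding; 149 per arm (85% of 175) gives 80.2%.

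**2. One test at 0.30 SD, no condition.** Φ(0.30/0.1010 − 2.241) = Φ(0.728) = 76.7%. This caps the joint power for a given analyte, since its birth test must reject first.

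**3. A given analyte significant at birth and at 4 months.** This is the bivariate normal probability that both z statistics exceed 2.241, with correlation 0.5 × √(147/n), where n is the number per arm at 4 months.

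| n per arm at 4 months | 4-month test alone | Birth and 4 months, 0.30 SD at both |
|---|---|---|
| 147 | 76.7% | 64.2% |
| 155 | 79.1% | 65.6% |
| 160 | 80.4% | 66.4% |
| 175 | 84.1% | 68.5% |

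With 147 per arm and equal effects, joint power is 80.2% at 0.345 SD, 81.6% at 0.35 SD and 92.4% at 0.40 SD.

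**4. Other meanings, 0.30 SD throughout, 147 per arm.**

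- 4-month test given that the same analyte rejected at birth: 0.642/0.767 = 84%.
- At least one analyte significant at both times: 87%, 83%, 80% and 74% for hemoglobin-ferritin correlation 0, 0.3, 0.5 and 0.8 (2,000,000 simulated draws).
- Both analytes at both times, as hypothesis 1 literally reads: 41%, 45%, 48% and 54% for the same correlations.

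**5. Error rate by reading of the opening rule.**

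- Same analyte only: two chains at 0.025 each, so at most 5% (1 − 0.975² = 4.94% if independent).
- Both birth tests required: also at most 5%.
- Either result opens both 4-month tests: above 5% only when exactly one analyte differs at birth and the other three nulls are true. At 0.31 SD and intraclass correlation 0.5 the simulated rate is 5.5-5.8% for hemoglobin-ferritin correlation 0.5 to 0, and 5.0% at 0.8. With near-certain detection at birth and independence it is 1 − 0.975³ = 7.3%; the bound is 3 × 0.025 = 7.5%.

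**The case against.** **The figure can be defended.** Because the sentence starts from the birth tests having to reject, it can be read as power at 4 months given a positive birth test. That is about 84% at 0.30 SD with 147 per arm, and the positive correlation does raise it. The at-least-one definition also reaches 80-87% over part of the correlation range. This stands: a reader might infer that the stated figure is simply false, and the documents do not support that. They leave the meaning open, and the figure fails on the per-analyte joint meaning.

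**The plan hedges and aims at 0.3 to 0.4 SD.** It says effect-size information is insufficient for explicit power estimates, and at 0.35-0.40 SD per-analyte joint power is 82-92%. So the inference that Aim 1 is underpowered and needs more infants does not follow. The 4-month sentence, however, attaches its figure to 0.3 SD.

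**The calculation is simplified.** One-sided testing at 0.025 would give 75% instead of 64%, still under 80%. The planned mixed model lets infants with only 4-month data add a little information at birth; with 175 per arm at 4 months, joint power at 0.30 SD rises from 68.5% to about 70%. Neither changes the conclusion.

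**The opening rule is nearly settled by the text.** Same-analyte is the natural sense of comparable. It fits the 0.025 split across two tests and the separate models, and it keeps 5%. A reader might infer that Aim 1 error is uncontrolled, since Primary Data Analysis omits the condition and four independent tests without it would give 1 − 0.975⁴ = 9.6%. That section does not revoke the condition, so the inference is not supported.

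**Conclusion.** The power point holds. At 0.30 SD at both times, with two-sided 0.025 and intraclass correlation 0.5, a given analyte has about a 64% chance of being significant at birth and at 4 months with 147 per arm, and about 69% with 175 at 4 months. Stated power above 80% needs a conditional definition, an at-least-one definition with hemoglobin-ferritin correlation no higher than about 0.5, or effects of at least about 0.345 SD. The plan names none of the first two, and its figure is stated from 0.3 SD upward. The two-sided level, the equal effects and the hemoglobin-ferritin correlation are assumptions.

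The opening-rule point is real but small. Under the natural reading 5% holds; under the loosest conditional reading the excess is at most 0.8 percentage points at the design effect, in one narrow configuration. Nothing here calls for a change in sample size or in the choice of primary tests.

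**What to change.** Replace the 4-month power sentence with one that names the definition (joint or conditional; given analyte or at least one), the 4-month sample size, the birth effect and the sidedness. For example:

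> For a given analyte, with 147 per arm at both times, intraclass correlation 0.5, two-sided 0.025 and equal effects, power to reject at birth and at 4 months is about 64% at 0.30 SD, 82% at 0.35 SD and 92% at 0.40 SD; power at 4 months given rejection at birth is about 84% at 0.30 SD.

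Use the 4-month sample size that the study expects. If at least one analyte is meant, say so and give the assumed hemoglobin-ferritin correlation.

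Before unblinding, put the same sentence in Sample Size and Primary Data Analysis:

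> Each analyte's 4-month test is confirmatory at 0.025 only if that same analyte's birth test is significant at 0.025.

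If both birth tests were meant to be required, state that instead; it also keeps 5%, but per-analyte power at 0.30 SD is then 49-54% for correlation 0 to 0.5.

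The cost is text only: no added data, visits or participants. The stated 4-month power will look less favorable, and an analyte cannot be claimed at 4 months on the strength of the other analyte's birth result.

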- Infant feeding practices measured via Infant and Child Feeding Index (ICFI)

¹ If no difference in iron status between *RAPIDIRON* treatment arms is detected at 12 months (once 12 month sample analysis is complete), we will no longer collect 24 month maternal blood samples.

Table 1. Schedule of RAPIDIRON-KIDS Study

Assessment Visit #	1	2	3	4	5	6
Age at Assessment	Birth	6 weeks	4 months	12 months	24 months	36 months
Iron Status						
Hemoglobin	X		XX	XX	XXX**	
Reticulocyte Hgb content	X		XX	XX	XXX	
Ferritin	X		XX	XXX	XXX	
%TSAT	X		XX	XXX	XXX	
Neurobehavioral						
Preferential Looking			X	X		
Ages & Stages Questionnaire 3				X		
Bayley Scales of Infant Development IV					X	X
Behavioral Rating Scale					X	
India Scale for Assessment of Autism						X
Child Behavior Checklist for Ages 1.5-5 (CBCL/1.5-5)					X	X
General Growth & Breastfeeding Practices						
Weight	X	X	X	X	X	X
Length	X	X	X	X	X	X
Head circumference	X	X	X	X	X	X
Breastfeeding	XXX	XXX	XXX	XXX	XXX	XXX
Infant Child Feeding Index (ICFI)	X	X	X	X	X	
Quality of life indices (WHODAS 2.0)						
Rates of hospitalization (post-delivery)						
Rates of transfusions (post-delivery)						

X = offspring**XX = offspring and mother****XXX = mother only**

	RAPIDIRON
	RAPIDIRON-KIDS

*Note: The RAPIDIRON study will provide much of the information for the first two visits (as made clear by the different color boxes and key). Cord blood is the source of iron status for Visit 1.

**See footnote on page 14.

As previously noted, if a participating mother experiences an intercurrent pregnancy within 36 months post-delivery, a blood sample will be collected and analyzed to obtain a complete set of iron indices.

Domains and Timing of Assessments

Primary Outcomes, Related Hypotheses, and Rationale:

(1) Iron status as indicated by hemoglobin and ferritin at birth and at 4 months of age

Hypothesis: Infants born to RAPIDIRON mothers from the IV iron arms will have higher hemoglobin and ferritin levels at birth and at 4 months of age compared to infants born to mothers in the oral iron arm.

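### Aim 1 keeps every test at a fixed 0.025 and never reuses the alpha of an analyte that has succeeded at both times: a valid rule, but one that gives up power within the 0.05 allowed

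*Combined protocol and SAP*

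**What the plan says.** All references are to the combined protocol and SAP.

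- **Error rate for the aim.** Section E, Sample Size, treats Aims 1 and 2 as separate questions: "the study is powered with a type I error rate of 0.05 for each of those aims".
- **Number of tests.** The same section says: "We propose to conduct a total of four primary hypothesis tests for Aim 1". These are hemoglobin and log ferritin, pooled IV arms against oral, at birth and at 4 months.
- **Split.** "To control the type I error rate across these two tests, the alpha level for each individual comparison will be 0.025". Section E, Primary Data Analysis, makes the comparison "with respect to the mean values at birth and at 4 months using a significance level of 0.025".
- **Gate.** "If either of those tests at birth show differences between the two arms, the comparable tests will be conducted at 4 months post-delivery". The power paragraph then says: "Since demonstrating the effects at 4 months requires that the hypothesis tests at birth reject the null hypothesis". Neither sentence makes clear whether a birth rejection opens only the 4-month test of the same analyte or both 4-month tests.
- **Hypothesis.** Section A says that infants in the IV arms "will have higher hemoglobin and ferritin levels at birth (determined by cord blood) and at 4 months of age", and Section D repeats the claim: "will have higher hemoglobin and ferritin levels at birth and at 4 months of age".

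There is no Holm, fallback, graphical or other rule that moves alpha within Aim 1, and no statement of whether Aim 1 succeeds on any or on all of the four tests.

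**The concern.** Suppose hemoglobin has been rejected at birth and at 4 months. With a same-analyte gate, the only nulls that can still be falsely rejected are those for ferritin, and they are tested at 0.025. The remaining 0.025 of the 0.05 for Aim 1 then protects nothing. It could be passed to the ferritin tests without raising the family-wise error above 0.05, and the same holds with the analytes exchanged.

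The second analyte bears the cost. It matters because Hypothesis 1 names both analytes at both times, and because power at the smallest planned effect is only about 80% per birth test before any gate is applied.

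**Working it through.** **Inputs from Section E, Sample Size.** 294 IV vs 147 oral; target effects 0.3 to 0.4 SD, with power quoted at 0.31 SD; intraclass correlation 0.5, used here as the birth-to-4-month correlation; alpha 0.025 per test.

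**Assumptions.** Two-sided tests, because the null is equality and sidedness is not stated. Equal effects for both analytes at both times. A hemoglobin-ferritin correlation of 0.3 (range 0 to 0.5), since the documents give none. 147 per arm at 4 months as well, although the plan expects slightly more.

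**The plan's own figure.** The effective size is 294 × 147 / 441 = 98. The expected z at 0.31 SD is 0.31 × √98 = 3.069. The two-sided critical value at 0.025 is 2.241. Power = Φ(3.069 − 2.241) = Φ(0.828) = 79.6%. The plan says more than 80%, so its figure is reproduced to within rounding.

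**Rules compared.**

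- *Fixed:* each analyte is tested at birth and, if rejected, at 4 months, always at 0.025.
- *Recycled:* the same two chains, but when both tests of one chain reject, the other chain is judged at 0.05.

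**Why recycling stays within 0.05.**

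- If true nulls lie in one chain only, the first of them is tested at 0.05 at most, and nothing later in that chain is reached unless it is rejected.
- If true nulls lie in both chains, neither chain can be completed without a false rejection. Until one occurs, the first true null in each chain is therefore tested at 0.025, and 0.025 + 0.025 = 0.05.

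Simulation over the patterns of true and false nulls agreed: the maximum was 0.05 within simulation error. Under the fixed rule, with one analyte truly responding at both times and the other not at all, the error was about 0.025.

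The trigger must be completion of the chain. If alpha were passed on after birth alone while the same analyte kept 0.025 for 4 months, the bound would be 0.025 + 0.05 = 0.075.

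**Power by simulation of four correlated z statistics, same-analyte gate.**

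| Scenario | Quantity | Fixed | Recycled |
|---|---|---|---|
| 0.31 SD, correlation 0.3 | each birth test | 79.5% | 83.8% |
| 0.31 SD, correlation 0.3 | each 4-month test, reached and rejected | 68.1% | 74.4% |
| 0.31 SD, correlation 0.3 | all four | 50.1% | 62.5% |
| 0.31 SD, correlation 0 | all four | 46.5% | 60.1% |
| 0.31 SD, correlation 0.5 | all four | 53.0% | 64.6% |
| 0.30 SD, correlation 0.3 | all four | 45.2% | 57.8% |
| 0.40 SD, correlation 0.3 | all four | 86.1% | 92.0% |

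At 0.31 SD and correlation 0.3, the chance of rejecting at least one birth test is 93.2% under both rules, and of at least one 4-month test 86.3% under both.

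**The other reading of the gate.** Suppose either birth rejection opens both 4-month tests, and only one birth null is false. Three true nulls are then each tested at 0.025, so the bound is 3 × 0.025 = 0.075; simulation gave about 0.07. In that pattern there is no unused alpha to pass on. The fixed-rule power for all four is the same under both readings, because rejecting all four at 0.025 opens either gate.

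**Related figure.** The plan states more than 80% power at 4 months for 0.3 SD. At 147 per arm the 4-month test alone has Φ(0.30 × √98 − 2.241) = Φ(0.729) = 76.7%. Requiring rejection at birth for the same analyte brings it to about 64%.

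**The case against.** - **A fixed split is legitimate.** This stands. With a same-analyte gate the family-wise error is at most 0.05, the split is prespecified, and the power statement is based on it. A reader might infer that the plan's error control is faulty; on that reading of the gate it is not.
- **The gate may be the wider one.** This stands in part. Against a gate where either birth rejection opens both 4-month tests, the two chains lower 4-month power: from 75.9% to 74.4% at 0.31 SD with equal effects (correlation 0.3), and from 66.8% to 28.4% for an analyte with only 0.15 SD at birth and 0.31 SD at 4 months. A reader might infer that recycling costs nothing for any test; that is true only relative to the same-analyte gate. The wider gate has its extra power because its error rate can reach about 0.07. Nor do the documents show that the plan does overspend, since the gate sentence can be read either way.
- **All-four power is not the plan's criterion.** This stands. A reader might take the wording of Hypothesis 1 as a rule that all four tests must reject, but the documents set no such rule, and the split with an either-test gate fits claims made analyte by analyte. If all four were required, no split would be needed: each could be tested at 0.05, with 63.7% power at 0.31 SD. Judged per test, the gain is about 4 points at birth and 6 at 4 months.
- **The gain shrinks with larger effects.** True: it is about 6 points for all four at 0.40 SD, and less than 2 for each birth test.

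**Conclusion.** The point holds as an efficiency improvement, not as a validity error. Relative to a same-analyte gate, the two-chain rule rejects everything the fixed rule rejects and sometimes more, with family-wise error still at most 0.05. The all-four gain at 0.31 SD is about 12 to 14 points over the assumed range of analyte correlation. It matters most near the bottom of the plan's 0.3 to 0.4 SD range and does nothing for the chance of at least one success. The sizes depend on equal effects at both times and on an analyte correlation that the documents do not give; the error bound depends on neither. The unclear gate has to be settled first, because recycling cannot simply be added to the wider reading.

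**What to change.** In Section E, Sample Size and Primary Data Analysis, before any unblinded analysis:

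1. State that the gate is same-analyte: a 4-month test is made only if the birth test of that analyte rejected.
2. Define two chains at 0.025 each: hemoglobin at birth then at 4 months, and log ferritin at birth then at 4 months. Only when both tests of one chain reject does its 0.025 pass to the other chain, whose tests are then judged at 0.05.
3. State whether Aim 1 claims are made analyte by analyte or require all four tests. If all four are required, test each at 0.05 without a split.
4. Restate power for each test and for all four, with the gate applied at 4 months, and state the sidedness and the assumed analyte correlation.

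The cost is SAP wording and a power recalculation, with no added participants, visits or samples. If the authors had intended the wider gate, they also give up some 4-month power, which is the price of keeping Aim 1 at 0.05.
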